### **Time to first down-titration of the study drug**

The time (day) to first down-titration is defined as the start date of first down-titration dosing interval minus the date of first dose plus one day. If no down-titration occurred for the patient, the time (day) to first down-titration will be censored on the date of death (if the patient died), or the date of last visit (if the patient did not die) for the patient.

For overall and for each stratum (ACEi, ARB, No RASi), the time (day) to first down-titration, will be summarized by treatment group, using Kaplan-Meier curves.

The SAF will be used for the above analyses.

### **Dose interruption**

A dose-interruption dosing interval is defined as a dosing interval whose dose level is 0.

The number and percentage of patients with at least one dose-interruption dosing interval will be provided by treatment group, for overall and for each stratum (ACEi, ARB, No RASi).

The duration of dose interruption is defined as the sum of (the end date minus the start date plus one day) among all dose-interruption dosing intervals.

The number and percentage of patients whose duration of dose interruption is larger than 14 days will be provided by treatment group, for overall and for each stratum (ACEi, ARB, No RASi).

The SAF will be used for the above analyses.

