## 2.4 Treatments (study treatment, rescue medication, concomitant therapies, compliance)

### 2.4.1 Study treatment / compliance

The study drug administration will be recorded on the CRF page: “Dosage Administration Record – Double-blind Medication” using start date, end date and dispensing level of the study drug. Each pair of start date and end date will be considered as a dosing interval.

For each patient, the dosing intervals will be sorted according to the start date and the end date from the earliest to the latest. It is expected that, for each patient, there should be no gaps and overlaps among dosing intervals, with the exception that, the end date of a dosing interval can be the same as the start date of its next dosing interval, when the patient may take the previous dispensing level in the morning and start a different dispensing level in the evening.

In the presence of gaps or overlaps, data conventional imputation algorithm will be applied to the start date and end date. Detailed algorithm will be provided in the study programming datasets specifications (PDS).

For patients who permanently discontinue from the study treatment, there should be a dosing interval with its start date equal to the date of the permanent discontinuation of the study drug, its end date equal to the study completion/discontinuation date, and its dispensing level equal to “No treatment”.

For each dosing interval, the dispensing level of the study drug will be recorded together with the start date and end date. The dose level and the daily dose (mg/day) are defined based on the dispensing level according to [Table 2-5](#).

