**Table 2-5 Dose levels and daily doses of the study drug**

Dispensing Level	Dose Level	Dose			Daily Dose		
		LCZ696	Valsartan	Enalapril	LCZ696	Valsartan	Enalapril
No treatment	0	No Dose	No Dose	No Dose	0 mg/day	0 mg/day	0 mg/day
Dose level 1	1	50 mg bid.	40 mg bid.	2.5 mg bid.	100 mg/day	80 mg/day	5 mg/day
Dose level 2	2	100 mg bid.	80 mg bid.	5.0 mg bid.	200 mg/day	160 mg/day	10 mg/day
Dose level 3	3	200 mg bid.	160 mg bid.	10.0 mg bid.	400 mg/day	320 mg/day	20 mg/day

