### **Duration of treatment**

The duration (day) of treatment is defined as the date of the last dose of the study drug minus the date of the first dose of the study drug plus one day, regardless of temporary treatment interruption.

The duration (week) of treatment will be converted from the duration (day) of treatment using a factor of 7 day/week, and will be summarized by treatment group, for overall and for each stratum (ACEi, ARB, No RASi), using number of observations, mean, standard deviation, median, minimum, Q1, Q3, and maximum.

The duration (week) of treatment will be categorized into the following categories.

- < 2 weeks
- 2 weeks to < 8 weeks
- 8 weeks to < 16 weeks
- $\geq$  16 weeks

The categorized duration of treatment will be summarized by treatment group, for overall and for each stratum (ACEi, ARB, No RASi), using the number and percentage of patients within each category.

Besides, the overall patient-weeks on-treatment will be provided by treatment group, for overall and for each stratum (ACEi, ARB, No RASi), where the overall patient-weeks on-treatment is defined as the sum of duration (week) of treatment among all patients within the corresponding treatment group and stratum.

The SAF will be used for the above analyses.

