### **Dose down-titration**

A down-titration dosing interval is defined as a dosing interval whose dose level is changed to a lower dose level from its previous dosing interval.

The dose down-titration will be summarized by treatment group, for overall and for each stratum (ACEi, ARB, No RASi), using the number and percentage of patients with at least one down-titration dosing interval.

The SAF will be used for the above analyses.

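### The SAP's dose-interruption rows also count permanent stops, because the closing off-drug interval is at dose level 0 and is not excluded

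*SAP*

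**What the plan says.** SAP section 2.4.1 builds all exposure outputs from dosing intervals, each with a start date, an end date and a dispensing level. For a permanent discontinuer, "there should be a dosing interval with its start date equal to the date of the permanent discontinuation of the study drug", with "its end date equal to the study completion/discontinuation date" and a dispensing level of No treatment. Table 2-5 ("Dose levels and daily doses of the study drug") gives No treatment dose level 0.

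Under Dose interruption, "A dose-interruption dosing interval is defined as a dosing interval whose dose level is 0". Two patient counts follow, by arm and stratum in the safety set: those with at least one such interval, and those whose interruption lasts more than 14 days in total. The total is "the sum of (the end date minus the start date plus one day) among all dose-interruption dosing intervals". Nothing requires dosing to resume, and the closing interval is not excluded.

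Under Dose down-titration, the counted interval is "a dosing interval whose dose level is changed to a lower dose level from its previous dosing interval". Time to the first one is "the start date of first down-titration dosing interval minus the date of first dose plus one day".

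**The concern.** A reader of an exposure table takes dose interruption to mean a pause in dosing. As defined, the rows mix pauses with permanent stops. Other parts of the SAP keep the two apart:

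- Duration of treatment runs from first to last dose "regardless of temporary treatment interruption".
- Duration on each dose level counts level-0 time only between the first and last dose. If the permanent stop falls on the day of the last dose, that day is not counted at level 0.
- Section 2.8.1 classifies adverse events with drug withdrawn separately from those with drug interrupted.
- Table 2-9 tabulates hyperkalemia leading to interruption and to permanent discontinuation as separate items.

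At stake is how a tolerability summary is read. If permanent discontinuation differs between arms, part of that difference can appear under the heading of interruption.

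**Working it through.** The plan states no figure for these rows, so there is none to reproduce. The check traces the rules and then applies the SAP's own day count.

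**Trace.** Permanent discontinuation leads to a closing No treatment interval (2.4.1, opening text). No treatment is dose level 0 (Table 2-5). Level 0 is a dose interruption (Dose interruption). No other SAP text removes the closing interval. The deferral to the programming specification in 2.4.1 covers gaps and overlaps between intervals, and the closing interval is neither.

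**One patient, two outputs.** Take first dose Day 1, no pause, last dose Day 56, stop date Day 57, study end Day 168 (the Week 24 visit in protocol Table 6-1).

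- Dose interruption: 168 − 57 + 1 = 112 days.
- Duration on each dose level: 0 days at level 0.
- Percentage of study drug exposure: 56/56 = 100%.

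**The 14-day row.** For a stop on Day d with follow-up to Day 168, the closing interval lasts 168 − d + 1 = 169 − d days.

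- d = 154: 15 days, so the patient enters the row on the closing interval alone.
- d = 155: 14 days, so not on the closing interval alone; 1 earlier level-0 day is needed.
- d = 160: 9 days; 6 earlier level-0 days are needed.
- In general, for d > 154, at least 15 − (169 − d) = d − 154 earlier level-0 days are needed.

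**Size.** Let p be the proportion of safety-set patients who permanently discontinue, and r the share of them who also had an earlier temporary level-0 interval. Those patients belong in the any-interruption row anyway, so the row rises by p(1 − r). The documents give neither p nor r, so the values below are assumptions.

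| Assumed p | r = 0 | r = 50% | r = 100% |
|---|---|---|---|
| 5% | 5 points | 2.5 | 0 |
| 10% | 10 points | 5 | 0 |
| 15% | 15 points | 7.5 | 0 |

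**Between arms (assumed).** Suppose true temporary interruption is 10% in both arms and p is 10% in one and 5% in the other. The reported rate is 10% + p(1 − r): 20% v 15% at r = 0, 15% v 12.5% at r = 50%, and 10% v 10% at r = 100%.

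The more-than-14-days row also rises by at most p. It rises by less if discontinuers leave the study soon after stopping or already exceed 14 days.

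**The case against.** The strongest reply is that the definition is explicit and may be deliberate. The heading says interruption, not temporary interruption, and the authors excluded the closing interval under Duration on each dose level, so they knew of it. Protocol section 5.6.2, on stopping study treatment, itself uses the word interruption when it describes registering such a patient. So the documents' vocabulary is not uniform, and a total-time-off-drug measure would be legitimate. But the SAP nowhere states that purpose, and an unlabelled row cannot convey it.

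The second reply is that little is lost, and most of it stands. Duration on each dose level and Percentage of study drug exposure already describe off-drug time without the closing interval. Permanent discontinuation has its own summaries in section 2.3.1 and by visit in 2.4.1. None of these, however, gives the number of patients who paused.

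A reader might infer that the down-titration count and Kaplan-Meier curve need the same exclusion, because a permanent stop from a positive dose level meets that definition too. The documents do not support this. Protocol section 5.5.5 places temporary discontinuation at the lower end of the same step-down sequence, so coding a move to level 0 as a step down is coherent. Ending follow-up at permanent discontinuation would also risk informative censoring, since patients may stop because they cannot tolerate the drug.

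**Conclusion.** The inconsistency is real and minor. As written, each safety-set patient with the closing interval that the SAP calls for enters the any-interruption row, and enters the more-than-14-days row when total level-0 time exceeds 14 days. The same patient can show 112 interruption days in one output and none at level 0 in another.

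The rise in each row lies between zero and the permanent-discontinuation proportion. The percentages above are illustrations under assumed rates. A reader might infer that the arm comparison must be distorted. It need not be: the any-interruption row does not change if every discontinuer had already paused, and it rises equally if p(1 − r) is the same in both arms. Nor does the point reach efficacy: only descriptive exposure rows are affected, and no hypothesis test, alpha allocation or estimate moves.

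**What to change.** Under Dose interruption, exclude the terminal permanent-discontinuation interval (level-0 time after the last dose, as under Duration on each dose level) from both the patient count and the summed duration. Keep all earlier temporary level-0 intervals. State how a pause that runs straight into a permanent stop is handled, so that programmers do not have to choose.

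For Dose down-titration and the time to the first one, at most add a footnote that any move to level 0, temporary or permanent, counts as an event. Leave the censoring rule as it is.

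The cost is a sentence or two in the SAP before database lock and some programming. No new data are needed.

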### **Compliance**

As presented in [Table 1-1](#), in this study, the study medication includes LCZ696 Active/Placebo (for all patients), Enalapril Active/Placebo (only for patients in the ACEi stratum) and Valsartan Active/Placebo (only for patients in the ARB stratum).

For each applicable study medication, the compliance will be recorded on the CRF page: “Study Treatment Compliance per Visit”, whereby, for each post-baseline scheduled visit (Week 2, Week 4, Week 8, Week 12, Week 16, Week 20 and Week 24), the compliance from the closest previous attended scheduled visit to the current visit should be recorded.

Specifically, for patients in the ACEi stratum, the compliance for LCZ696 Active/Placebo and Enalapril Active/Placebo will be recorded; for patients in the ARB stratum, the compliance for LCZ696 Active/Placebo and Valsartan Active/Placebo will be recorded; for patients in the No RASi stratum, the compliance for LCZ696 Active/Placebo will be recorded.

For each patient and each post-baseline scheduled visit, the on treatment duration (day) from the closest previous attended scheduled visit to the current visit is defined as the number of days on any positive dose level during the period from the date of the closest previous attended scheduled visit (inclusive for the first post-baseline scheduled visit, but exclusive for all afterwards) to the date of the current visit (inclusive).

For each patient and each applicable study medication (Table 1-1), the overall compliance for the study medication is defined as the weighted mean of the compliance using the on treatment duration (day) as the weight, i.e.

$$\frac{\sum_k \text{On Treatment Duration (day) in Period } k \times \text{Compliance (\%)} \text{ in Period } k}{\sum_k \text{On Treatment Duration (day) in Period } k},$$

where period  $k$  is the period from the date of the closest attended scheduled visit prior to Visit  $k$  (inclusive for the first post-baseline scheduled visit, but exclusive for all afterwards) to the date of Visit  $k$  (inclusive), and the sum is over all attended post-baseline scheduled visit.

For each stratum (ACEi, ARB, No RASi) and each applicable study medication (Table 1-1), the overall compliance (%) will be summarized separately by treatment group, using number of observations, mean, standard deviation, median, minimum, Q1, Q3, and maximum.

#### 2.4.2 Prior and concomitant therapies

Prior and concomitant medications will be recorded on the CRF page: “Prior and Concomitant Medications”. Procedures and significant non-drug therapies (prior and concomitant) will be recorded on the CRF page “Surgical and Medical Procedures”.

The missing or partially missing start/end date for prior/concomitant therapies will be imputed based on the Novartis ADaM Governance Board (AGB) global standards.

Prior and concomitant medications/non-drug therapies will be identified based on recorded or imputed start dates and end dates.

Prior medications are defined as any recorded medication with its start date (recorded or imputed) prior to the date of the first dose of the study drug.

Concomitant medications are defined as any recorded medication with its end date (recorded or imputed) later than or equal to the date of the first dose of the study drug AND its start date (recorded or imputed) prior to or equal to the end date of the study.

Prior non-drug therapies are defined as any procedure/significant non-drug therapy with its start date (recorded or imputed) prior to the date of the first dose of the study drug.

Concomitant non-drug therapies are defined as any recorded procedure/significant non-drug therapy with its end date (recorded or imputed) later than or equal to the date of the first dose of the study drug AND its start date (recorded or imputed) prior to or equal to the end date of the study.

For overall and for each stratum (ACEi, ARB, No RASi), prior and concomitant medications will be summarized separately by treatment group, anatomical therapeutic classification (ATC) and PT; prior and concomitant non-drug therapies will be summarized separately by treatment group, SOC, PT.

In addition, for each of the following classes, prior medications and concomitant medications will be summarized by treatment group, for overall and each stratum (ACEi, ARB, No RASi).

- Open label ACEi
- Open label ARB
- Open label ACEi or ARB
- Open label dual RAS blockade
- Open label sacubitril/valsartan
- Renin inhibitors
- Beta blockers
- Diuretics
  - Aldoesterone antagonists
  - Loop diuretics
  - Thiazide diuretics
  - Other diuretics
- Calcium antagonists
- Nitrates
- Other vasodilators
- Cardiac glycosides (digoxin/digitalis glycoside)
- Antiarrhythmic agents
- Aspirin
- Other antiplatelet agents
- Other antithrombotic agents
  - Vitamin-K antagonist
  - NOAKs
- Statins
- Other lipid lowering agents
- Insulins
- GLP-1 agonists
- Oral anti diabetics
  - SGLT-2 inhibitors

The SAF will be used for the above analyses.

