Screening NT-proBNP, complete lab evaluations, and pregnancy testing will be assessed by sending samples to the central lab. It may take up to 72 hours to obtain the results of the clinical laboratory assessments to evaluate the patient’s eligibility for the study.

Qualifying echocardiogram (echo) measurements will be based on locally obtained echoes performed within 6 months of Visit 1. If a qualifying echo within 6 months of Visit 1 is not available, the patient must enter the study based on a qualifying echo performed during the screening epoch before any study drug is dispensed to the patient. No imaging method other than echocardiography will be accepted for inclusion into the study.

KCCQ questionnaire will be administered at screening to determine eligibility for study (CSS < 75). A 6MWT will be performed at screening in all patients to familiarize patients with the assessment.

A patient who enters screening but is determined not to be eligible will be considered a screen failure. The investigator may consider re-screening the patient at a later time if he/she believes that the patient's condition has changed and they may potentially be eligible. A patient may be re-screened once. A minimum of 2 weeks must elapse between screen failure and re-screening.

Randomized treatment epoch

At the randomization visit (Visit 101), all patients who fulfill the inclusion/exclusion criteria will be stratified based upon prior therapy as described above. Subsequent to stratification, patients will be randomized into either the LCZ696 or the comparator treatment group at a 1:1 ratio. [Table 3-1](#) categorizes low and high total daily doses for commonly used ACEis and ARBs. Study drug dose levels are outlined in [Table 3-2](#) and study drug up-titration outlined in [Figure 3-2](#). The goal of treatment is to ensure that each patient receives the maximal tolerated dose of study medication.

[figure not shown]
ACEis are required to be discontinued 36 hours prior to the randomization visit (Visit 101) to minimize potential risk of angioedema, and ARBs are required to be discontinued at the randomization visit. With the exception of ACEi, ARB or renin inhibitor, patients will continue on their prior medication for the treatment of comorbidities. All patients must be on stable doses of appropriate therapy for comorbidities for at least 4 weeks prior to enrollment.

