3.6 Risks and benefits

Patients will be instructed not to take any other RAS blockade medications (ACEi, ARB or renin inhibitor) except study drug (LCZ696, enalapril, or valsartan) to avoid excess RAS blockade and minimize potential risk of angioedema. Washout of prior RAS agents is ensured by the discontinuation of prior ACEis at least 36 hours prior to randomization and discontinuation of prior ARBs on the day of randomization. If the patient is to be started on open-label ACEi during the study, study drug will be stopped \geq 36 hours prior to initiating ACEi treatment. All patients will continue other individualized medical therapy for comorbidities as directed by the investigator. The risk to patients in this trial will be minimized by compliance with the eligibility criteria, study procedures, and close clinical monitoring (eg hypotension).

In women of child-bearing potential, a possible risk of developmental toxicity cannot be excluded. Women of child-bearing potential should therefore, use a highly effective method of contraception during dosing and for 7 days after stopping of study medication. If there is any question that the patient will not reliably comply, they should not be entered in the study. All patients in this study will be \geq 45 years of age and therefore the risk of pregnancy during the trial is minimal.

Clinical trial data in adults demonstrate that LCZ696 has an overall safety profile generally comparable to other RASi agents. For patients participating in this study: the risks common to LCZ696, enalapril and valsartan include hypotension, hyperkalemia, worsening renal function and angioedema. Potential risks of LCZ696 also include hepatotoxicity, effects on bone growth and mineralization, and changes in amyloid beta in the central nervous system (CNS).

Participating patients will benefit from careful monitoring and follow-up during the entire study duration regardless of whether they are receiving the study medication.

4 Population

The study population will consist of patients \geq 45 years of age with a LVEF $>$ 40% and evidence of structural heart disease (LAE and/or LVH), current symptoms of HF (NYHA class II-IV), use of diuretics within the prior 30 days, NT-proBNP $>$ 220 pg/mL for patients with no AF or $>$ 600 pg/mL for patients with AF, and KCCQ CSS $<$ 75. Eligible patients will be on appropriate medical therapy for comorbidities in the opinion of the investigator.

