9.3 Treatments

The overall duration on the randomized study drug will be summarized by treatment group using mean, standard deviation, median, minimum, and maximum. Additionally, the number and percentage of patients will be summarized by treatment group for duration category. Mean doses and dose levels will be summarized by treatment group and visit.

Concomitant medications and significant non-drug therapies, prior to and after the randomization date respectively, will be summarized by therapeutic class, preferred term, and treatment group for the SAF.

The number and percentage of patients on different CV background medications (eg mineralocorticoid receptor antagonist, β -blockers, diuretics, and digoxin) will be tabulated by treatment at baseline and during the randomized treatment epoch.

The FAS will be used for the above analyses unless otherwise specified.

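### The same-day boundary in the SAP's concomitant-medication rule can count a prior ARB, stopped on schedule at randomization, as open-label ARB use during treatment

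*SAP*

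**What the plan says.** SAP 2.4.2 sets two date conditions for a concomitant medication. It must be "any recorded medication with its end date (recorded or imputed) later than or equal to the date of the first dose of the study drug". The second condition is that it has "its start date (recorded or imputed) prior to or equal to the end date of the study". Nothing requires the drug to have been started after study drug began. The prior category is defined separately and does not exclude the concomitant one: "Prior medications are defined as any recorded medication with its start date (recorded or imputed) prior to the date of the first dose". The same section then lists drug classes to be summarized as prior and as concomitant, by treatment group, overall and within each stratum. The list includes *Open label ARB* and *Open label ACEi or ARB*. The analysis set is the SAF.

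The protocol fixes when earlier RAS inhibitors stop. Section 3.1 says "ARBs are required to be discontinued at the randomization visit", and section 3.6 likewise has "discontinuation of prior ARBs on the day of randomization". ACE inhibitors must stop 36 hours before that visit. Table 3-3 heads its initiation column with Visit 101, and Table 6-1 has study medication first dispensed at Visit 101, Day 1.

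Protocol 9.3 describes the split more loosely: "Concomitant medications and significant non-drug therapies, prior to and after the randomization date respectively" are to be summarized. It gives no rule for a record that ends on the boundary day.

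**The concern.** Stopping an ARB at Visit 101 and starting study drug that day is what the protocol asks for. Under the SAP rule that patient appears in the concomitant open-label ARB rows alongside a patient who was put on an ARB in mid-study. The two mean opposite things: one followed the protocol, and the other had an exposure that Protocol 5.5.8 prohibits while study drug is being taken and that 5.5.5 answers by withdrawing study drug.

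The class summary in SAP 2.4.2 is the only output the SAP names that shows how often open-label RAS inhibitors were used, by arm and stratum. If scheduled stops fill those rows, a reader of the study report cannot separate contamination from compliance. The rule would also create an artificial contrast between strata, because scheduled ACE-inhibitor stops fall outside it.

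**Working it through.** The documents give no figure for this point, so there is nothing to reproduce. The check has two parts.

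**1. Apply the rule to dates.** Let R be the randomization date. The drug began long before R.

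| Case | Prior? | Concomitant under SAP 2.4.2 (end ≥ first dose)? | With a strict rule (end > first dose)? |
|---|---|---|---|
| ARB ends R, first dose R | yes | **yes** | no |
| ARB ends R, first dose R+1 | yes | no | no |
| ARB ends R−1, first dose R | yes | no | no |
| ACEi ends R−1 or R−2, first dose R | yes | no | no |

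Only the first row is caught. It is an expected path: Protocol 5.5.4 places doses at about 08:00 and 19:00, so a morning ARB tablet, a clinic visit and an evening dose of study drug all fall on one date. A stop 36 hours before the visit puts the ACE-inhibitor end date on R−1 or R−2, so compliant ACEi patients are never caught.

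**2. Size in the ARB stratum.** Let f be the share of ARB-stratum patients whose ARB end date equals the first-dose date, and x the true share with later open-label ARB use. Neither is in the documents. Both are assumed here and taken as independent.

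- Tabulated share = 1 − (1 − f)(1 − x)
- Part due to scheduled stops alone = f(1 − x)

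With x = 5%:

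| f | Tabulated share | Due to scheduled stops alone |
|---|---|---|
| 0 | 5% | 0 |
| 0.25 | 1 − 0.75 × 0.95 = 28.75% | 23.75 points |
| 0.50 | 1 − 0.50 × 0.95 = 52.5% | 47.5 points |
| 0.75 | 1 − 0.25 × 0.95 = 76.25% | 71.25 points |
| 0.90 | 1 − 0.10 × 0.95 = 90.5% | 85.5 points |
| 1 | 100% | 95 points |

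The result depends little on x. At f = 0.5 the row reads 51% for x = 2% and 55% for x = 10%, so an eight-point difference in real use would show as four.

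The all-strata column is inflated by the ARB share of the trial times f(1 − x). Protocol 3.1 sets no stratum proportions. If the ARB share is assumed to be 30% to 50%, then at f = 0.5 and x = 5% the overall row rises by 0.30 × 47.5 = 14.25 to 0.50 × 47.5 = 23.75 points.

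**The case against.** The strongest reply is that two dates must coincide and the documents fix neither. SAP 2.1.1 keeps the randomization date and the first-dose date apart, and the first dose after a clinic visit may be taken that evening or the next morning. The protocol says when the ARB is to be discontinued, but not whether the recorded end date is the visit day or the day of last intake. This stands, and it is why the size is given as a range that starts at no effect. A reader might infer that most ARB-stratum patients will be misclassified; the documents do not support that.

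It can also be said that the summary is correct under its own definition, and that counting a drug taken on the first-dose day as concomitant is a defensible choice for a safety set. The SAP's treatment-emergent AE rule likewise includes the first-dose day. That too is fair. The difficulty lies in what the open-label RASi rows will be taken to show.

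Three stronger readings are tempting and should not be drawn:

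- *That efficacy results are affected.* H1 to H4 do not use the flag. The on-treatment analysis in SAP 2.5.4 has its own trigger, open-label RASi or LCZ696 after permanent discontinuation. Table 5-1 lists no per-protocol exclusion for open-label ARB. Prior ARB use precedes randomization, so no systematic difference between arms is expected.
- *That the table would show dual RAS blockade.* A single prior ARB does not fill the open-label dual-blockade row, and blinded study drug is not open label.
- *That the SAP contradicts the protocol while declaring no change.* Protocol 9.3 does not classify the boundary day, and filling in such detail is the SAP's job.

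The protocol-deviation summary in SAP 2.3.1 might also capture prohibited medication, but its full criteria are in a data review plan that is not part of these documents.

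**Conclusion.** The point holds as a defect in one descriptive summary. Followed exactly, SAP 2.4.2 places a compliant ARB-stratum patient with coinciding dates in the concomitant *Open label ARB* and *Open label ACEi or ARB* rows, and never does so for a compliant ACEi-stratum patient.

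That conclusion rests on the text alone. Its size rests on f and x, which are assumptions: from no inflation at f = 0 to a row made up mainly of scheduled stops once half or more of the dates coincide. Because f is unknown, the rows cannot be read as open-label ARB use during treatment whatever they turn out to show. No inference about treatment effect changes. The case for acting is that the problem can be foreseen, it obscures the frequency of a prohibited exposure, and it is very cheap to remove before database lock.

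**What to change.** In SAP 2.4.2, for the open-label RASi rows only:

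- Count a record as on-study if its start date is on or after the first-dose date, **or** its end date is strictly later than the first-dose date. Keep the existing end-of-study limit.
- Show records that started before first dose and ended on the first-dose date as prior only.
- Add a separate row for open-label RASi started after first dose.

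Compared with the present rule, the first condition removes only records with start date before, and end date equal to, the first-dose date. A record that both starts and ends on the first-dose date is kept, which a bare change from ≥ to > on the end date would lose. A prior ARB wrongly continued past the first-dose date also stays counted, and the added row separates it from new starts.

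The cost is a sentence or two in the SAP, one programming condition and one extra table row, using data already collected. The downside is that a last prior-ARB intake on Day 1 appears as prior use only. The change concerns tabulation and alters no clinical rule.
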